5. Package containing blinded study drug supply, study journals (medicine log, symptom tracker and experience log) and study documents (details on aims, design, consent forms, and any additional instructions) are delivered to the address provided by participant as place of residence during study. Delivery of blind study drug supply will occur in two shipments, each containing a 30-day supply. Day 1 is defined as the first day the blinded study drug is taken by the participant.
6. Each day active medication is taken (HCQ or placebo), participants will record 1) temperature (to be reported twice daily, either via thermometer or self-report); 2) time medication taken; and 3) any symptoms and AEs.
7. Every week, clinical research coordinators will review the study portal to assess for AEs and indication of reported symptoms indicative of influenza like illness. The research coordinator will also review self-reported fever and/or temperature. If COVID-19 symptoms are evident, the research coordinator will outreach to the HCW (at clinic or by phone). Clinical research coordinators may clinically escalate any medical determinations to Co-PI following study portal review.
8. The HCW also has access to the study coordinators via the study phone number. If the HCW feels symptomatic, then he/she should call the clinical research coordinator team, and document symptoms in the study portal. Clinical research coordinators may clinically escalate any medical determinations to Co-PI.
9. If during the study symptoms indicative of an influenza like illness present, participant will be asked to comply with their employer's potential or confirmed COVID-19 incident protocol and be tested for COVID-19 by an accepted method. Participants negative for COVID-19 continue with the assigned blinded study drug regimen.
10. If confirmed COVID-19 diagnosis, participant will be unblinded. Participants assigned to HCQ can continue with medication schedule. Individuals assigned to the placebo arm will be offered the opportunity to cross-over to HCQ 600 mg daily for 14 days. Individuals will be expected to continue self-reporting temperature, time medication taken and any symptoms/AEs into the study portal while taking active HCQ medication.
11. Participants who remain undiagnosed for COVID-19 by the end of the medication period (Day 60) will be asked to undergo COVID-19 and serology testing for IgM/IgG on either Day 61, 62, or 63.

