COVID-19/SARS-CoV-2 testing: Upon the presentation of symptoms indicative of an influenza like illness, participants will be asked to undergo testing for SARS-CoV-2 virus. Participants undiagnosed for COVID-19 at Day 60 will also be tested for SARS-CoV-2 and IgM/IgG antibodies (via serology testing) on either Day 61, 62, or 63.

Clinical Symptom monitoring: The study team will assess AEs, symptoms, and record temperature (either reported temperature or self-report of fever) for any participants taking active medication (placebo or HCQ). Worsening COVID symptoms and/or new or worsening AE's will be reviewed by the PI's for causality to study drug. The rate of conversion to receiving a positive COVID-19 test result in each arm at the 2-month mark will be used to assess the primary endpoint.

Pill count and Journal: Participants will be contacted to compare data entry on the portal and collect any missed entries over the phone.

Participants will be instructed to call 911 upon immediate presentation of the following symptoms as identified by the CDC as requiring emergency action: bluish lips or face; new confusion/dizziness or inability to arouse; persistent pain or pressure in the chest (not caused by coughing); and difficulty breathing (including severe shortness of breath and single word speech).

Participant confidentiality is strictly held in trust by all personnel granted access to the trial data. Therefore, the study data, and all other information generated will be held in strict confidence. No information concerning the study, or the data will be released to unauthorized parties.

The study investigators and study team, the research sponsor and its designees, personnel from ProHealth with authorized access to study data, government agencies, reviewing Institutional Review Board (IRB), regulatory agencies and/or company supplying study product may inspect all documents and records required to be maintained by the sponsor, including but not limited to, clinical, pharmacy and lab records for participants enrolled in the study. All applicable parties will permit access to such records.

The participant's study contact information will be securely stored within the online study portal for internal use during the study. At the end of the study, all records will continue to be kept in a secure location for as long as dictated by the reviewing IRB and institutional policies.

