9.2 Adverse Events Reporting Period

The study period during which adverse events must be reported is defined as the period from the initiation of the first study treatment to the last administration of study treatment.

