9.3 Adverse Events Post Study

All unresolved adverse events at the conclusion of the dosing period should be followed by the investigator until the event is resolved, the participant is lost to follow-up, or the adverse event is otherwise explained. At the last scheduled contact, the study staff should instruct each participant to report any subsequent event(s) that the participant, or the participant's personal physician, believes might reasonably be related to participation in this study.

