9.4 Adverse Events Assessment and Recording

At each contact with the participant, the investigator or study staff will assess for information on adverse events and review all self-reported AE's via the study portal. Information surrounding adverse events should be recorded in the study portal. Related signs, symptoms, and abnormal diagnostic procedures results should be recorded in the study portal and grouped under one diagnosis as applicable.

Adverse events can be spontaneously reported or elicited during open-ended questioning. Adverse events will be measured and graded in accordance with the document entitled *Division of AIDS (DAIDs) Table for Grading the Severity of Adult and Pediatric Adverse Events, Corrected Version 2.1, July 2017* issued by the US Department of Health and Human Services. The clinical course of each event should be followed until resolution, stabilization, or until it has been determined that the study treatment or participation is not the cause. Serious adverse events that are still ongoing at the end of the study period must be followed up to determine the final outcome. Any serious adverse event that occurs after the study period and considered to be at least possibly related to the study treatment or study participation should be recorded and reported immediately.

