10.0 SERIOUS ADVERSE EVENTS

A serious adverse event is any AE that is:

- fatal
- life-threatening
- requires or prolongs hospital stay
- results in persistent or significant disability or incapacity
- a congenital anomaly or birth defect
- a suspected transmission of an infectious agent (e.g., pathogenic or nonpathogenic) via the study drug
- an important medical event
- All Serious Adverse Events (SAEs) that occur following the participant’s written consent to participate in the study must be reported, whether related or not related to study drug. If applicable, SAEs must be collected that relate to any later protocol-specified procedure.
- Following the participant’s written consent to participate in the study, all SAEs, whether related or not related to study drug, are collected, including those thought to be associated with protocol-specified procedures. The investigator should report any SAE occurring after these aforementioned time periods, which is believed to be related to study drug or protocol-specified procedure.
- An SAE report should be completed for any event where doubt exists regarding its seriousness;
- If the investigator believes that an SAE is not related to study drug but is potentially related to the conditions of the study (such as withdrawal of previous therapy or a complication of a study procedure), the relationship should be specified in the narrative section of the SAE Report Form.

All SAEs should be followed to resolution or stabilization. Serious adverse events that are ongoing at the end of the study period must be followed to determine the outcome. Any serious adverse event that occurs after the study period and is at least possibly related to the study treatment or study participation should be recorded and reported immediately to the Medical Monitor and the IRB per the IRB reporting guidelines.

PATCH 2 & 3 TRIAL

All adverse events that do not meet any of the criteria for serious should be regarded as non-serious adverse events.

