15.0 MEASUREMENT OF EFFECT

15.1 Definitions

Evaluable for toxicity: All participants will be evaluable for toxicity from the time of their first treatment with HCQ or placebo through final assessment.

Evaluable for primary outcome: Participants who received at least one continuous week of HCQ will be evaluable for the primary outcome.

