15.2 Response Criteria

PATCH 2 (Sub-Study 1): Measurement of SARS-CoV-2 positivity confirmed by an accepted testing method. Rate of hospitalization will be defined by a hospitalization occurring within 30 days of the date of participant enrollment.

PATCH 3 (Sub-Study 2): Rate of COVID-19 infection will be defined by measurement of SARS-CoV-2 identified by accepted testing methods.

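### PATCH 3: routine reporting after a COVID-19 diagnosis follows study-drug dosing and so differs by arm (minor; secondary outcomes only)

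*Combined protocol and SAP*

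**What the plan says.** Section 4.0, PATCH 3, item 6 asks for the daily record on each day that study medication is taken. Under item 10, a confirmed diagnosis unblinds the participant. HCQ participants may then carry on with their schedule, and placebo participants are offered HCQ 600 mg daily for 14 days. Reporting after diagnosis is described as: "Individuals will be expected to continue self-reporting temperature, time medication taken and any symptoms/AEs into the study portal while taking active HCQ medication".

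Two other sections tie observation to dosing. Section 8.4 has the study team assess AEs and symptoms "for any participants taking active medication (placebo or HCQ"). Section 9.2 gives the AE reporting period as "defined as the period from the initiation of the first study treatment to the last administration of study treatment". Section 7.3 sets treatment at up to 60 days, with closing tests on Days 61–63 for undiagnosed workers only.

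Other text reaches further. Section 15.1 states: "All participants will be evaluable for toxicity from the time of their first treatment with HCQ or placebo through final assessment". Section 9.3 requires that "All unresolved adverse events at the conclusion of the dosing period should be followed by the investigator until the event is resolved", and section 9.4 that "The clinical course of each event should be followed until resolution, stabilization". Section 10.0 says that after consent "all SAEs, whether related or not related to study drug, are collected". Items 7 and 8 of section 4.0 add weekly coordinator review of the portal and a phone line.

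On the outcomes, section 15.2 says "Rate of hospitalization will be defined by a hospitalization occurring within 30 days of the date of participant enrollment", but in its PATCH 2 paragraph. The PATCH 3 paragraph defines infection only. Section 16.2 plans an odds ratio for hospitalisation and rate ratios for AEs and missed shifts in PATCH 3.

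**The concern.** COVID-19 admissions, symptoms and missed shifts mostly arise after diagnosis. From that point, how long a worker is routinely asked about them depends on the assigned arm, the diagnosis date and, for placebo workers, whether crossover is accepted. A between-arm contrast in AEs or admissions can then partly reflect how long people were asked.

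There is a second, separate problem. Section 16.2 counts AEs by participant and averages them by group, with no rule for events after crossover. If groups are the randomised arms, AEs that occur on open-label HCQ are counted for placebo, which blurs the safety comparison that the rate ratio is meant to give.

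**Working it through.** The plan gives no figure to reproduce here, so the check is day arithmetic on the stated rules.

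**Inputs.** From section 16.1: 175 per arm, with infection rates of 10% (placebo) and 1% (HCQ). From sections 4.0 and 7.3: dosing to Day 60, crossover for 14 days. Assumed: diagnosis day *d* is uniform over Days 1–60; crossover starts at once; HCQ workers continue to Day 60; 50–100% of infections surface before the Day 61–63 tests.

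**Workers affected.** Placebo 0.10 × 175 = 17.5; HCQ 0.01 × 175 = 1.75; total 19.25. At 50% surfacing: 8.75 + 0.875 = 9.6. So about 10 to 19, with fewer than two on HCQ.

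**Routine reporting days after diagnosis.** An HCQ continuer has 60 − *d*; a crossover participant has 14.

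| Diagnosis day | HCQ continues | Placebo crosses over |
|---|---|---|
| 10 | 50 | 14 |
| 30 | 30 | 14 |
| 46 | 14 | 14 |
| 55 | 5 | 14 |
| 60 | 0 | 14 |

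The HCQ mean is 29.5 days. The order reverses after Day 46.

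**Cover of a fixed horizon.**
- First 30 days, HCQ: mean of min(30, 60 − *d*) = (30 × 30 + 435)/60 = 22.25 days, or 74%. Crossover: 14/30 = 47%.
- First 14 days, HCQ: mean of min(14, 60 − *d*) = (46 × 14 + 91)/60 = 12.25 days, or 88%. Crossover: 100%.
- Diagnoses on Days 31–60, 30-day horizon: HCQ 435/30 = 14.5 days, or 48%. Crossover: 47%.

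**Whole-arm shortfall in placebo**, against 175 × 60 = 10,500 participant-days:
- All diagnosed workers cross over: 17.5 × (29.5 − 14) = 271 days (2.6%). At 50% surfacing: 8.75 × 15.5 = 136 days (1.3%).
- All decline, so that reporting stops at diagnosis: 17.5 × 29.5 = 516 days (4.9%). At 50% surfacing: 8.75 × 29.5 = 258 days (2.5%).

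**Open-label HCQ days counted for placebo.** If all cross over: 17.5 × 14 = 245 of the 10,500 − 271 = 10,229 placebo reporting days (2.4%). At 50% surfacing: 8.75 × 14 = 122.5 of 10,364 (1.2%).

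**Sections 9.2 and 15.1.** For an undiagnosed PATCH 3 worker the two end points differ by 1–3 days (last dose Day 60, test Days 61–63). For a diagnosed worker the readable text schedules no final assessment, so the end point in 15.1 is undefined.

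**The case against.** The strongest reply is that a worker still ill when dosing ends is already covered in both arms. Section 9.1 counts intercurrent illness as an AE, 9.3 and 9.4 require it to be followed, and 10.0 collects serious AEs regardless of relatedness. Section 8.4 also lets PATCH 3 participants report AEs by phone with no on-drug condition, and the Appendix 4 reminder card asks workers to track hours missed through COVID-19 symptoms. Item 10 says when portal entries are expected; it does not end contact. This largely stands and is why the point is minor. What remains is that these rules set no common schedule of routine contact. Section 8.4 makes PATCH 3 AE capture depend wholly on self-report, and the weekly review in item 7 reads the portal.

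A second reply is that section 14.0 places the schedule of events in the process flows, which could not be read. That stands too: the point is limited to the readable text, and a flow chart may set a contact schedule after diagnosis.

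A reader might also infer more than the documents support:
- *Diagnosed workers are lost to follow-up.* Sections 9.3, 9.4 and 10.0 say otherwise.
- *HCQ workers are always observed longer, so the bias has a known sign.* The order reverses for diagnoses after Day 46 and over the first 14 days.
- *Sections 9.2 and 15.1 contradict each other in a way that loses safety data.* One defines a reporting period and the other evaluability, the PATCH 3 gap is 1–3 days for undiagnosed workers, and 9.3 partly bridges it.
- *The missing PATCH 3 hospitalisation window is a serious defect in itself.* It is a missing detail, best settled in the same amendment.

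**Conclusion.** The point holds as a minor one. In the readable text, routine PATCH 3 reporting follows dosing. After diagnosis it therefore differs by arm, and AEs on open-label crossover HCQ would be counted for placebo. At planning rates this touches at most about 19 workers, with a placebo reporting shortfall of 1.3–2.6% of participant-days if all diagnosed placebo workers cross over, and up to 4.9% if none do. These figures rest on the assumed uniform diagnosis day and surfacing range. They count reporting days, not missed events, and the 30-day contrast of 74% with 47% depends on the chosen horizon.

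The direction of any bias is unknown. A reader might infer that the primary result is at risk. It is not, because a diagnosed worker already has the primary event. Section 16.2 also reports secondary outcomes without significance tests.

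**What to change.** - **Sections 4.0 (items 6 and 10) and 8.4:** every randomised PATCH 3 participant reports AEs, admissions and missed shifts to Day 63, whether or not on study drug. Diagnosed participants continue for a fixed period after diagnosis, for example 30 days, if that ends later.
- **Sections 9.2 and 15.1:** use the end of that window as the end of the PATCH 3 AE period and as the final assessment.
- **Section 15.2:** define the PATCH 3 hospitalisation rate over the same window and count all admissions, including any that section 10.2 exempts from AE reporting.
- **Section 16.2:** tabulate AEs after the first open-label HCQ dose separately from the randomised comparison.
- Bring the process flows into line.

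The cost is amendment wording and a few extra portal entries or calls: up to three more days for those who complete dosing, the remaining days for those who stop early, and up to Day 90 for a worker diagnosed on Day 60 (60 + 30). No new tests or visits are needed.

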5.0 RANDOMIZATION

[figure not shown]
Randomization will be done using computer generated randomization numbers. Randomization will be stratified by age. Treatment **will start upon receipt of the product by the patient after enrolling in the study, notifying the pharmacy and having the product/placebo sent.**

Blinding: Both sub-studies will have a double-blind placebo-controlled design.

Unblinding: (*See study process flows*)

- For PATCH 2 (Sub-study 1), If patient in PATCH 2 experiences worsening of symptoms, a Co-PI will be notified to take appropriate clinical action. Co-PI can choose to unblind for clinical determinations.
- For PATCH 3 (Sub-Study 2), confirmation of a COVID-19 diagnosis would trigger the unblinding pathway for a participant (for details see *Section 4.0, Participant Registration, PATCH 3 (Sub-Study 2) Participant Procedure*).

Figure 1. Schematic of PATCH 2 and PATCH 3 Study Designs

6.0 TREATMENT PLAN

PATCH 2 (Sub-Study 1) 500 patients with 2 interim analyses

- *Arm 1 (HCQ):* Hydroxychloroquine 400 mg bid (two 200 mg tablets taken twice a day; totaling 800 mg per day) for 14 days
- *Arm 2 (Placebo):* Two pills taken twice daily (totaling four pills each day) for 14 days

PATCH 3 (Sub-Study 2) 350 participants with 2 interim analyses

- *Arm 1 (HCQ):* Hydroxychloroquine 600 mg qd (three 200 mg tablets taken once day) for 60 days
- *Arm 2 (Placebo):* Three pills once a day for 60 days with optional crossover to HCQ 600 mg qd for 14 days upon presentation of symptoms indicative of an influenza like illness and subsequent confirmatory diagnosis for COVID-19

7.0 DETAILS OF STUDY TREATMENT

7.1a Hydroxychloroquine

Mechanism of Action: The mechanism of action is not fully understood. Previously it was thought that HCQ and other chloroquine derivatives are weak bases that deacidify lysosomes through purely chemical basis. Recently our group has identified the missing molecular target of HCQ as palmitoyl protein thioesterase 1 (PPT1).

PATCH 2 & 3 TRIAL

Storage and formulation: HCQ tablets are manufactured by a number of generic drug companies as well as Novartis. Each tablet contains 200 mg hydroxychloroquine sulfate (equivalent to 155 mg base). It is dispensed in a tight, light-resistant container as defined in the USP/NF. HCQ should be stored at room temperature up to 30° C (86° F).

Pharmacokinetics: The PK of HCQ is characterized by a large volume of distribution, binding to red blood cells, and long time to peak concentration and steady state. Population PK studies in cancer patients have demonstrated dose proportional change in exposure.

Administration: Hydroxychloroquine is an oral medication available in 200 mg tablets. HCQ will be supplied by the study team via Avella Pharmacy. Tablets of HCQ are available in 200 mg strength. In PATCH 2 (**Sub-Study 1**), HCQ will be administered in divided doses (every 12 hours) with each dose consisting of two 200 mg tablets (or 400 mg bid), totaling 800 mg daily. **The two daily doses of HCQ should be taken 12 hours apart, for example, 9 am and 9 pm.** In PATCH 3 (**Sub-Study 2**), HCQ will be administered as three 200 mg tablets taken once a day (600 mg qd) at the same time. Hydroxychloroquine sulfate tablets should be taken with a meal or a glass of milk. Participants will be required to keep a study journal and document the time HCQ doses are taken; journal completion will be reviewed by study staff. The HCQ schedule may be adjusted if necessary, to minimize gastrointestinal side effects.

For complete information please refer to the package inserts at <http://dailymed.nlm.nih.gov/dailymed/>

7.1b Placebo

There will be no active medication in the placebo tablets, which will be supplied by the study team via Avella Pharmacy and mailed to the participant's provided address. In PATCH 2 (Sub-Study 1), placebo will be administered in two divided doses (every 12 hours) with each dose consisting of two tablets, totaling four tablets daily. The two daily doses of placebo should be taken 12 hours apart, for example, 9 am and 9 pm. In PATCH 3 (Sub-Study 2), placebo will be administered as three tablets taken once a day at the same time. Tablets should be taken with a meal or a glass of milk. Participants will be required to keep a study journal and document the time placebo doses are taken. The dosing schedule may be adjusted if necessary, to minimize, gastrointestinal side effects. Journal completion will be reviewed by study staff.

7.2 Concomitant Medication, Drug-Drug interactions and Procedures

Participants will be instructed not to take any medications, including over the counter products, without first consulting with the study team. The study phone number and additional contact information will be provided with the welcome packet, allowing for the study team to be contacted if the participant is seen by a health care provider or medications are changed.

Drug Interactions

Insulin or antidiabetic drugs: As HCQ may enhance the effects of a hypoglycemic treatment, a decrease in doses of insulin or antidiabetic drugs may be required.

Drugs that prolong QT interval and other arrhythmogenic drugs: HCQ can prolong the QT interval and should not be administered with other drugs that have the potential to induce cardiac arrhythmias. Also, there may be an increased risk of inducing ventricular arrhythmias if HCQ is used concomitantly with other arrhythmogenic drugs.

Antiepileptics: The activity of antiepileptic drugs might be impaired if co-administered with HCQ.

PATCH 2 & 3 TRIAL

Cyclosporin: An increased plasma cyclosporin level was reported when cyclosporin and HCQ were co-administered.

Because HCQ has known effects on P450 enzymes, participants requiring anti-convulsants may be treated with any of the non-enzyme inducing anti-convulsants which include: felbamate, valproic acid, gabapentin, lamotrigine, tiagabine, topiramate, or levetiracetam. Due to the fact that both zonisamide and HCQ accumulate in red blood cells, zonisamide should be avoided if possible. Other concomitant medications may be permitted.

The following medications and treatments are not allowed during the study. The sponsor must be notified if the participant receives any of these during the study:

1. PATCH 2 and 3 (**Sub-Studies 1 and 2**): Any investigational or off-label antiviral therapy
2. Any concurrent chemotherapy, radiotherapy, immunotherapy, biologic or hormonal therapy for cancer treatment, except as noted in the exclusion criteria. Concurrent use of hormones for noncancer-related conditions (e.g. insulin for diabetes, hormone replacement therapy) is acceptable.
3. Immunosuppressive medications, including, corticosteroids at doses exceeding 10mg/day of prednisone or equivalent, methotrexate, azathioprine, and TNF-alpha blockers. Use of immunosuppressive medication for the management of study treatment-related AEs or in subjects with contrast allergies is acceptable. In addition, use of topical, inhaled and intranasal corticosteroids is permitted
4. Live attenuated vaccines during the study through 180 days after the last dose of both drugs

7.3 Duration of Protocol Treatment and Follow-up.

PATCH 2 (Sub-Study 1) duration of treatment is 14 days (two weeks) with follow-up with COVID-19 testing on Day 15, 16 or 17, and Day 29, 30 or 31 where Day 1 marks the first day blinded study drug is taken by the participant.

PATCH 3 (Sub-Study 2) duration of treatment is up to 60 days with an option to cross-over for participants taking placebo upon presentation of symptoms indicative of an influenza like illness and testing positive for COVID-19 (or a COVID-19 diagnosis is made by a health care provider). Participants remaining undiagnosed for COVID-19 by Day 60 will undergo testing for SARS-CoV-2 and IgM/IgG antibodies on either Day 61, 62, or 63. The maximum study medication duration and follow-up testing is 63 days.

7.4 Crossover from Control to HCQ arm.

PATCH 2 (Sub-Study 1): There is no cross-over.

PATCH 3 (Sub-Study 2): Participants that develop symptoms indicative of an influenza like illness and diagnosed with COVID-19 will be unblinded. If they were assigned to the placebo arm and deemed appropriate, they will be offered the option crossover to HCQ 600 mg qd for 14 days.

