PATCH 3 Inclusion (Sub-Study 2): Currently employed as a health care worker ([name]; Doctor of Osteopathic Medicine, DO; Nurse Practitioner, NP; Physician's Assistant, PA; and [name] or other members of the medical care team with significant COVID-19 exposure); asymptomatic and presumed negative for COVID-19 (no confirmatory testing conducted); scheduled for an average of ≥ 20 hours per week of clinical care over the next two months (or equivalent indicating at least part-time employment). Participant will be asked to comply with their employer's potential or confirmed COVID-19 incident protocol and must agree to undergo COVID-19 testing per standard of care using an FDA approved method upon the presentation of symptoms indicative of an influenza like illness; if a confirmatory COVID-19 diagnosis is given, participant will be offered to cross-over to HCQ 600 mg qd for 14 days. At the end of the 60-day medication period, participants remaining undiagnosed for COVID-19 will undergo virus and serology testing. (See Appendix- PATCH3 process flows)

PATCH 2 & PATCH 3 Combined Exclusion Criteria

(See Study Exclusions and Content Job Aid)

- Allergy to hydroxychloroquine, 4 aminoquinolines, or quinine
- Known G6PD deficiency
- Pregnant or lactating or intention of becoming pregnant during the study as self-reported during enrollment screening
- Receiving any trial treatment drug for 2019-nCoV within 14 days prior to screening evaluation (off label, compassionate use or trial related)
- Known retinal disease including but not limited to macular degeneration, retinal vein occlusion, visual field defect, diabetic retinopathy
- History of interstitial lung disease severe emphysema or asthma, or chronic pneumonitis Current diagnosis of porphyria or psoriasis
- Serious intercurrent illness that requires active intravenous therapy, intense monitoring, or frequent dose adjustments for medication including but not limited to infectious disease, cancer, autoimmune disease, cardiovascular disease

PATCH 2 & 3 TRIAL

- Have undergone major abdominal, thoracic, spine or CNS surgery in the last two months, or plan to undergo surgery during study participation
- Is receiving cytochrome P450 enzyme-inducing anticonvulsant drugs (i.e. phenytoin, carbamazepine, Phenobarbital, primidone or oxcarbazepine) within four weeks of the start of the study treatment
- Currently taking digoxin
- History or evidence of increased cardiovascular risk including any of the following:

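### PATCH 3: section 7.3 accepts a provider diagnosis in place of a positive test as the crossover trigger, against section 4.0, and a worker diagnosed that way also falls outside exit testing

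*Combined protocol and SAP*

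**What the plan says.** All section references are to the combined protocol and SAP.

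**Crossover and unblinding trigger**
- Section 7.3 makes crossover available after symptoms and "testing positive for COVID-19 (or a COVID-19 diagnosis is made by a health care provider".
- Section 4.0, PATCH 3 procedure, item 9: symptomatic workers are tested by an accepted method, and "Participants negative for COVID-19 continue with the assigned blinded study drug regimen".
- Section 4.0, item 10: "If confirmed COVID-19 diagnosis, participant will be unblinded. Participants assigned to HCQ can continue with medication schedule". Placebo workers are then offered 14 days of HCQ.
- Section 5.0: "confirmation of a COVID-19 diagnosis would trigger the unblinding pathway for a participant". It sends the reader to 4.0 for details.
- Section 6.0 requires symptoms and a "subsequent confirmatory diagnosis for COVID-19".
- Section 7.4 unblinds symptomatic workers who are diagnosed and offers crossover where deemed appropriate. It does not say whether the diagnosis needs a test.

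**Exit testing**
- Section 3.1: "participants remaining undiagnosed for COVID-19 will undergo virus and serology testing". Section 4.0 item 11, 7.3 and 8.4 restrict the Day 61-63 test in the same way.

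**Reporting after crossover**
- Section 4.0 item 10 expects workers to "continue self-reporting temperature, time medication taken and any symptoms/AEs into the study portal while taking active HCQ medication", which for a crossed-over worker is 14 days.

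**Primary endpoint**
- Sections 1.1, 8.4 and 15.2 all require a positive result from an accepted test.

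**The concern.** For a worker with a positive test, unblinding and crossover follow the primary event and cannot affect it. For a worker with only a provider diagnosis they come first. That worker is still at risk for the test-based endpoint, now knows the assignment, may be taking HCQ after randomization to placebo, and counts as diagnosed, so the Day 61-63 test no longer applies. A missed or false-negative swab is one of the things that test might still have picked up.

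Follow-up can also differ by arm. Workers assigned to HCQ may carry on with their 60-day schedule, while a crossed-over placebo worker is asked to report only during the 14 days of HCQ.

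At stake are avoidable unblinding, some contamination of the placebo arm, and uneven ascertainment of the primary endpoint. Staff also cannot follow both rules for a swab-negative worker whom a provider diagnoses.

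**Working it through.** **Step 1. The texts side by side.** Take a symptomatic worker with a negative swab and a clinical diagnosis of COVID-19.

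| Question | 4.0 items 9-11 | 7.3 |
|---|---|---|
| Stay on blinded drug? | Yes | Not if the provider diagnosis is acted on |
| HCQ offered if on placebo? | No | Yes |
| Day 61-63 test? | Yes, if the negative result leaves the worker undiagnosed | No, the worker is diagnosed |
| Primary event recorded? | Only if a later test is positive | Only if a later test is positive, and none is scheduled |

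The conflict with item 9 is direct. With 5.0 and 6.0 it rests on the ordinary meaning of confirmation, which 4.0 supports. Section 7.4 fits either rule.

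**Step 2. The plan's own power figure.** Section 16.1 gives 175 per arm, 10% versus 1%, one-sided alpha 0.05 and at least 80% power.
- Pooled z: SE under the null = sqrt(2 × 0.055 × 0.945 / 175) = 0.0244. SE under the alternative = sqrt((0.10 × 0.90 + 0.01 × 0.99) / 175) = 0.0239. Power = Φ((0.09 − 1.645 × 0.0244) / 0.0239) = 98.2%.
- Log odds ratio: ln 11 = 2.398; SE = sqrt((1/0.09 + 1/0.0099) / 175) = 0.800. Power = Φ(2.398/0.800 − 1.645) = 91.2%.

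The 80% holds as a lower bound. No standard 80% formula tried gave 350, but that does not bear on this point. Planned events are 17.5 + 1.75 = 19.25, and the planned odds ratio is (0.01/0.99)/(0.10/0.90) = 0.0909.

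**Step 3. Scenario A: the provider diagnosis is wrong and the worker is still at risk.** The documents give no rate, so assume 2%, 5% or 10% of all workers, diagnosed at Day 30, half of them on placebo.
- Workers affected: 350 × 0.02, 0.05, 0.10 = 7, 17.5, 35. On placebo: 3.5, 8.75, 17.5.
- Constant hazards: h0 = −ln(0.90)/60 and h1 = −ln(0.99)/60.
- Remaining placebo risk as planned: 1 − exp(−30 h0) = 5.13%.
- Risk still counted, with HCQ working as the plan assumes on Days 31-44 and nothing ascertained afterwards: 1 − exp(−14 h1) = 0.23%.
- Placebo events lost: 4.90% × 3.5, 8.75, 17.5 = 0.17, 0.43, 0.86 of 17.5.
- Placebo rate: 9.90%, 9.76%, 9.51%. Odds ratio: 0.092, 0.093, 0.096.
- Power from exact binomial enumeration of the pooled z at the final bound 1.6664: 99.3%, 99.2%, 99.0%.

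**Step 4. Scenario B: the provider diagnosis is right but never test-confirmed.** Assume a share f of infections in both arms goes unrecorded, giving rates 0.10(1 − f) and 0.01(1 − f).

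| f | Events lost of 19.25 | Odds ratio | Power, pooled z, exact, final look | Power, log odds ratio, normal approximation |
|---|---|---|---|---|
| 0 | 0 | 0.091 | 99.3% | 90.8% |
| 10% | 1.9 | 0.092 | 98.8% | 87.8% |
| 25% | 4.8 | 0.093 | 97.2% | 81.8% |
| 50% | 9.6 | 0.095 | 88.4% | 66.2% |

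Simulating all three looks with the stated bounds (44, 88 and 175 per arm) gives almost the same pooled-z values: 99.3%, 98.8%, 97.2% and 88.4%, or 88.2% at f = 50% if the futility bounds are followed. A three-look simulation of the log-odds-ratio z, with 0.5 added to each cell, gives 98.1% at f = 10%, 93.4% at 30% and 77.1% at 50%. The normal approximation is weak with only 1.75 expected HCQ events.

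**The case against.** The strongest reply is that the trigger is settled almost everywhere else. The synopsis, 3.1, 4.0, 5.0 and 6.0 speak of confirmation, often straight after a reference to testing, and 5.0 defers to 4.0. The outlier is one parenthesis in a section on duration, and it does not say that the provider diagnoses without a test; it may mean a diagnosis reported from outside the study. All symptomatic workers are meant to be tested, so the problem needs a skipped swab or a provider overriding a negative one. The PATCH 3 cross-over flow is a figure not available here and may name the trigger. Much of this stands. The confirmed rule is probably the intended one. But 7.3 offers the provider diagnosis as an alternative to a positive test, and a figure would not remove those words.

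Three stronger readings are tempting, and the documents do not support them.
- A reader might infer that the plan counts such a worker as a non-event. It says nothing on this. The worker has no recorded event under a positive-test endpoint, but could equally be treated as missing or excluded, and the evaluability rule in 15.1 also bears on who is analyzed.
- A reader might take 7.4 as a second statement of the wider rule. Its wording is ambiguous and adds a judgment of appropriateness.
- A reader might assume that exit serology would restore the lost events. Neither 8.4 nor 15.2 says that antibody positivity is a primary event. Workers also enter without confirmatory testing, so antibodies at exit would not by themselves date the infection to the trial.

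Scenario A is also pessimistic about ascertainment after Day 44, because symptom-triggered testing and the study phone line are not withdrawn.

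**Conclusion.** The inconsistency is real and its consequence is specific: followed literally, 7.3 can unblind a never-positive worker, offer a placebo worker HCQ, and remove the exit test before any primary event, with no rule for classifying that worker.

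The likely size is small. Over the assumed 2% to 10% of workers, fewer than one placebo event is lost and the odds ratio stays at or below 0.096. Even when a quarter of infections go unrecorded in both arms, power stays above 80% by every method applied at that share. It falls below 80% only at one half, and only with the log-odds-ratio statistic (77% simulated, 66% by approximation; 88% with the pooled z). These results rest on assumed frequencies, on equal shares in the two arms, and on the plan's 10% versus 1%. The case for change is that the defect is avoidable and cheap to remove. It does not threaten the planned power.

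**What to change.** **Preferred.** Delete the parenthesis in 7.3 and state one trigger for unblinding and crossover, a positive SARS-CoV-2 test by an accepted method, in the same words in 4.0, 5.0, 6.0, 7.3 and 7.4. Check the cross-over flow against it. The cost is wording, with one clinical downside: a placebo worker with a clinical diagnosis and no positive test gets no study HCQ.

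**If provider diagnosis is kept.** Replace *undiagnosed* by *without a positive test* in 3.1, 4.0 item 11, 7.3 and 8.4, so that every never-positive worker has the Day 61-63 test whether crossed over or not. On the assumed 2% to 10%, that is about 7 to 35 more tests of a kind the trial already performs, with no added participants. What serology then contributes to the primary analysis depends on whether antibody positivity counts as an event, so 8.4 and 15.2 should say so.

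Under this second option, also state how a provider-diagnosed, never-positive worker enters the primary logistic regression.
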